3.8. Analysis Visit Windows

3.8.1. Definition of Study Day

Study day will be calculated from the first dosing date of study drug and derived as follows:

- For postdose Study days: Assessment Date First Dosing Date + 1
- For days prior to the first dose: Assessment Date First Dosing Date

Therefore, Study Day 1/ First Dose Date is the day of first dose of study drug administration, as recorded on the Study Drug Administration eCRF.

Last Dose Date is defined as the maximum, nonmissing, nonzero dose end date of treatment recorded on the Study Drug Administration eCRF form with "Study Drug Permanently Withdrawn" box checked for participants who prematurely discontinued or completed study drug according to the Study Drug Completion eCRF. Refer to Section 12 for missing date imputation, if necessary.

Last Study Date is the latest of the study drug start dates and end dates, the clinic visit dates, and the laboratory visit dates, including the 30-day follow-up visit date, for participants who prematurely discontinued study according to the Study Completion eCRF.

Baseline value is defined as the last nonmissing value obtained on or prior to the first dose date (and time, if available) unless otherwise specified.

3.8.2. Analysis Visit Windows

Participant visits might not occur on protocol-specified days. Therefore, for the purpose of analysis, observations will be assigned to analysis windows.

The analysis windows for vital signs, respiratory, hematology and chemistry laboratory parameters are presented in Table 3-1 and Table 3-2.

Table 3-1.Analysis Windows for Vital Signs (Heart Rate, Temperature, Blood
Pressure [MAP if available, Systolic and Diastolic], Respiratory Rate,
and Oxygen Saturation)

Visit ID	Nominal Day	Lower Limit	Upper Limit
Baseline/Day 1	1		1
Day 2	2	2	2
Day 3	3	3	3
Day 4	4	4	4
Day 5	5	5	5
Day 6	6	6	6
Day 7	7	7	7
Day 8	8	8	8
Day 9	9	9	9
Day 10	10	10	10
Day 30	30	25	35

Table 3-2.Analysis Windows for Hematology, Chemistry, Urinalysis, and
Routine Coagulation Tests

Visit ID	Nominal Day	Lower Limit	Upper Limit
Baseline/Day 1	1		1 (pre dose)*
Day 2	2	1 (post dose)*	3
Day 5	5	4	6
Day 8	8	7	8
Day 10	10	9	11
Day 30 **	30	25	35

* For Baseline, the upper limit includes values collected at or prior to the first dose date/time. For Day 2, the lower limit includes values collected after the first dose date/time on Day 1.

** Only the comprehensive metabolic panel will be collected on Day 30

Nasopharyngeal and oropharyngeal samples (combined) OR nasal and oropharyngeal samples (combined), and rectal or fecal swab will be collected on Days 1, 3, 5, 7, and 10 (if feasible) for SARS-CoV-2 reverse transcriptase quantitative polymerase chain reaction (RT-qPCR) viral load testing and possible viral resistance testing. Endotracheal tube aspirates will also be collected if the participant is intubated. If the participant is discharged prior to Day 10, the samples for SARS-CoV-2 RTqPCR viral load testing and possible viral resistance testing can be collected by assigned study staff at the participant's home or as an outpatient on the assigned days noted above, if feasible.

Serum for SARS-CoV-2 IgG, IgM, and IgA serology will be collected at Screening, Day 5, Day 10 (if feasible), and the Day 30 Follow-up visit for participants with weight \geq 12 kg.

The analysis windows for SARS-CoV-2 RT-qPCR viral load and serology for SARS-CoV-2 are presented in Table 3-3 and Table 3-4.

Table 3-3.	Analysis Windows for SARS-CoV-2 RT-aPCR Viral Load Test	ting

Visit ID	Testing	Nominal Day	Lower Limit	Upper Limit
Baseline/Day 1	SARS-CoV-2 RT-qPCR viral load	1		1 (pre dose)
Day 3	SARS-CoV-2 RT-qPCR viral load	3	2	3
Day 5	SARS-CoV-2 RT-qPCR viral load	5	4	5
Day 7	SARS-CoV-2 RT-qPCR viral load	7	6	8
Day 10	SARS-CoV-2 RT-qPCR viral load	10	9	11
Discharge*	SARS-CoV-2 RT-qPCR viral load	Day of discharge		

* If the participant is discharged prior to Day 10, the SARS-CoV-2 samples/swabs will be collected on the day of discharge. Thereafter, these samples can be collected by assigned study staff at the participant's home or as an outpatient on the assigned days noted above.

Table 3-4.	Analysis Windows	for Serology for SAR	S-CoV-2 (IgG, IgM, and IgA)
	•		

Visit ID	Testing	Nominal Day	Lower Limit	Upper Limit
Baseline/Day 1#	Serology for SARS-CoV-2 (IgG, IgM, and IgA)	1		1 (pre-dose)
Day 5	Serology for SARS-CoV-2 (IgG, IgM, and IgA)	5	4	6
Day 10	Serology for SARS-CoV-2 (IgG, IgM, and IgA)	10	9	11
Discharge*	Serology for SARS-CoV-2 (IgG, IgM, and IgA)	Day of discharge		
Day 30	Serology for SARS-CoV-2 (IgG, IgM, and IgA)	30	25	35

Includes the serum for SARS-CoV-2 IgG, IgM, and IgA serology collected at Screening.

* If the participant is discharged prior to Day 10, the serology for SARS-CoV-2 will be collected on the day of discharge. Thereafter, these samples can be collected by assigned study staff at the participant's home or as an outpatient on the assigned days noted above.

Clinical scoring using the PEWS (0 to 3 on each of 3 categories) will be recorded at Screening and daily through the duration of dosing. Results will be summarized for each Study Day without windows.

The 7-point Ordinal Scale is an assessment of the clinical status of a given Study day. Each day, the worst (ie, lowest ordinal) score from the previous day will be recorded (ie, on Day 3, the

lowest ordinal score from Day 2 is obtained and recorded for Day 2). Results will be summarized for each Study Day without windows.

3.8.3. Selection of Data in the Event of Multiple Records in an Analysis Visit Window

Depending on the statistical analysis method, single values may be required for each Study Day or analysis window. For example, change from baseline by visit usually requires a single value, whereas a time-to-event analysis does not require 1 value per Study Day or analysis window.

If multiple valid, nonmissing measurements exist for a Study Day/analysis window, records will be chosen based on the following rules if a single value is needed:

- For baseline, the last nonmissing value on or prior to the first dosing date (and time, if available) of study drug will be selected, unless specified differently. If there are multiple records with the same time or no time recorded on the same day, the baseline value will be the average of the measurements for continuous data, or the measurement with the lowest severity for categorical data.
- For postbaseline values (other than PCR negative confirmation):
 - The record collected on the day closest to the nominal day will be selected.
 - If there are 2 days equidistant from the nominal day, the later day will be selected.
 - If there is more than 1 record on the selected day, values will be selected for analysis as follows:
 - For PCR, if there is more than 1 record on the selected day, the latest value will be selected. If there are multiple records with the same time or no time recorded on the same day, the geometric mean value (copies/mL) will be taken.
 - For other parameters, if there is more than 1 record on the selected day, the average will be taken for continuous data and the worst severity will be taken for categorical data, unless otherwise specified.
- For postbaseline values of PCR negative confirmation:
 - Use all available data to derive negative confirmation except if there are multiple records on the same day in which case the worst value will be used for negative confirmation for that day.
 - The record closest to the nominal day for that visit will be selected.
 - If there are 2 records that are equidistant from the nominal day, the later record will be selected.

4. SUBJECT DISPOSITION

4.1. Subject Enrollment and Disposition

Key study dates (i.e., first participant screened, first paticipant enrolled, last participant enrolled, and last participant last visit for the CSR) will be provided.

A summary of participant enrollment will be provided by cohort for each country, investigator and overall total. The summary will present the number and percentage of participants enrolled. For each column, the denominator for the percentage calculation will be the total number of participants analyzed for that column.

A summary of participant disposition will be provided by cohort and overall total for all screened participants. This summary will present the number of participants screened, the number of participants who met all eligibility criteria but were not enrolled along with the reasons the participants were not enrolled, the number of participants enrolled, the number of participants enrolled but never treated, the number of participants in the Safety Analysis Set, and the number of participants in the FAS.

For the status of study drug and study completion and reasons for premature discontinuation, the number and percentage of participants in each category will be provided. The denominator for the percentage calculation will be the total number of participants in the Safety Analysis Set corresponding to that column. In addition, a flowchart will be provided to depict the disposition.

The following by-participant listings will be provided by subject ID number in ascending order to support the above summary tables:

- Reasons for premature study drug or study discontinuation
- Reasons for screen failure (will be provided by screening ID number in ascending order)

4.2. Extent of Study Drug Exposure and Adherence

Extent of exposure to study drug will be examined by summarizing the number of doses received by cohort and overall total for the Safety Analysis Set.

A by-participant listing of study drug administration will be provided by subject ID number (in ascending order) and visit (in chronological order).

4.3. Protocol Deviations

A by-participant listing will be provided for those participants who did not meet at least 1 eligibility (inclusion or exclusion) criterion, or took prohibited medications from Screening to the Day 30 Follow-up visit, including:

- Investigational agents for COVID-19 with direct antiviral effect including approved HIV protease inhibitors such as lopinavir (LPV)/ ritonavir (RTV), chloroquine, interferon, etc.
- Strong inducers of P-glycoprotein (e.g. rifampin, rifabutin, carbamazepine, phenytoin or herbal medications)

Protocol deviations occurring after participants entered the study are documented during routine monitoring. The number and percentage of participants with important protocol deviations, and the total number of important protocol deviations by deviation category (e.g., eligibility criteria, informed consent) will be summarized by cohort and overall total for the Safety Analysis Set. A by-participant listing will be provided for those participants with important protocol deviations.

5. **BASELINE CHARACTERISTICS**

5.1. Demographics and Baseline Characteristics

Participant demographic variables (i.e., age, sex, race, and ethnicity) and baseline characteristics (i.e., body weight [in kg], body weight-for-age z-scores, height [in cm], height-for-age z-scores, body mass index [BMI; in kg/m2], BMI-for-age percentiles, BMI-for-age z-scores) will be summarized by cohort and overall total using descriptive statistics for continuous variables and using number and percentage of participants for categorical variables. The summary of demographic data will be provided for the Safety Analysis Set. No formal statistical testing is planned.

A by-participant demographic listing, including the informed consent date, will be provided by subject ID number in ascending order. Note: If information on Apgar score for participants < 24 hours of life and/or gestational age and birth weight for participants < 56 days of age has been collected this information will be listed.

5.2. Other Baseline Characteristics

The following other baseline characteristics will be summarized by cohort and overall total using descriptive statistics for continuous variables and number and percentage of participants for categorical variables.

- Oxygen support status at baseline based on the 7-point ordinal scale: (a) invasive mechanical ventilation, (b) non-invasive ventilation or high flow oxygen, (c) low flow oxygen, and (d) room air
- Clinical status (7-point ordinal scale)
- COVID-19 symptoms (respiratory, gastrointestinal, neurological, circulatory, systemic inflammatory response)
- Duration of hospitalization prior to first dose of RDV (days)
- Duration of symptoms prior to first dose of RDV (days)
- SARS-Cov-2 viral load (log10 copies)
- Aspartate aminotransferase (AST) (U/L)
- Alanine aminotransferase (ALT) (U/L)
- Electrocardiogram (ECG) (normal, abnormal [not clinically significant, clinically significant])

- Creatinine (mg/dL)
- Estimated glomerular filtration rate (eGFR) using the Bedside IDMS-traceable Schwartz formula (mL/min/1.73 m²)

The summary of these baseline characteristics will be provided for the Safety Analysis Set. No formal statistical testing is planned.

A by-participant listing of other baseline characteristics will be provided by subject ID number in ascending order.

5.3. Medical History

Medical history will be collected at screening for general conditions (i.e., conditions not specific to the disease being studied). It will be coded using the current version of Medical Dictionary for Regulatory Activities (MedDRA).

A summary table will present the number and percentage of participants reporting each medical history preferred term, sorted first in alphabetical order by system organ class (SOC) and then by preferred term (PT) in descending order of total frequency within SOC for each cohort and overall total for the Safety Analysis Set. No formal statistical testing is planned.

6. **EFFICACY ANALYSES**

6.1. Primary Efficacy Endpoint

There is no primary efficacy endpoint in this study.

6.2. Secondary Efficacy Endpoints

6.2.1. Definition of Secondary Efficacy Endpoints

Clinical improvement based on scoring using the 7-point Ordinal Scale

Clinical improvement improvement based on scoring using the 7-point Ordinal Scale will be derived as follows:

- If a participant dies while hospitalized (as recorded on the Death Report eCRF and Hospitalization Information eCRF), the endpoint on the day of death and all subsequent days through Day 10 will be set to Death (=1).
- If the participant is discharged alive, the endpoint on the day of discharge alive and all subsequent days through Day 10 will be set to Not hospitalized (=7).
- If the participant is discharged alive and dies on the same day or a later day (as recorded on the Death Report eCRF and Hospitalization Information eCRF), the endpoint on the day of discharge alive and all subsequent days until the day of death will be set to Not hospitalized (=7). On the day of death and all subsequent days through Day 10, the endpoint will be set to Death (=1).

Every effort will be made to obtain clinical status data for all participants prior to discharge alive. The last known clinical status will be used for days with missing clinical status (eg, where the reason for Hospital Discharge is not "Discharged Alive" and the participant has not died). All postbaseline days with missing ordinal scale score, from Day 2 to Day 10, will use the previous last known clinical status.

Clinical improvement is investigated in two settings:

- ≥ 1 point improvement from baseline clinical status or discharged alive
- \geq 2-point improvement from baseline clinical status or discharged alive on the 7-point ordinal scale

Recovery is defined as an improvement from a baseline score of 2 through 5 to a score of 6 or 7, or an improvement from a baseline score of 6 to a score of 7.

Clinical improvement based on scoring using the PEWS Improvement Scale

Clinical improvement is investigated in two settings:

- ≥ 1 point improvement from baseline clinical status or discharged alive
- \geq 2-point improvement from baseline clinical status or discharged alive on the 7-point ordinal scale

Recovery is defined as an improvement from a baseline score of 1-3 to a score of 0, or being discharged alive, whichever comes first.

Time (days) to discharge from hospital

- Duration of hospitalization from Day 1 = number of days from first dose to date discharged alive.
- Total duration of hospitalization = number of days from hospital admission to date discharged alive.

Oxygen usage and ventilation modality and settings

Oxygen support status is defined based on the 7-point ordinal scale.

Days to the first confirmed negative PCR result

• Confirmed negative PCR result is defined as 2 consecutive negative PCR results or a negative PCR result at the last available sample for participants who completed or discontinued from this study.

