6.2.2. Analysis of Secondary Endpoints

The FAS will be the primary analysis set for secondary efficacy endpoints. No formal statistical testing is planned.

Clinical improvement based on scoring using the 7-point Ordinal Scale

For each cohort and overall total, clinical status and change from Baseline in clinical status by Study Day as well as last available assessment will be summarized by the number and percentage of participants for each category. It should be noted that the main timepoint of interest for this endpoint is Day 10. In addition, a stacked bar chart will also be provided for each cohort and overall total depicting the percentage of participants for each category by Study Day. Furthermore, descriptive statistics for change from Baseline in clinical status by Study Day and last available assessment will also be provided for each cohort and overall total. Time to clinical improvement (days) will be modelled using a competing risk analysis. The competing event is death. Participants not achieving clinical improvement at the last assessment will be censored on the day of the last clinical assessment. In addition, the cumulative incidence from the competing risk analysis will also be graphically presented. The number and percentage of participants with clinical improvement will also be summarized by cohort and overall total.

Time to \geq 1-point improvement from baseline clinical status or discharged alive on the 7-point ordinal scale will be modelled using a competing risk analysis. The competing event is death. Participants not achieving \geq 1-point improvement at the last assessment will be censored on the day of the last clinical assessment. In addition, the cumulative incidence from the competing risk analysis will also be graphically presented. Furthermore, the number and percentage of participants with a \geq 1-point improvement or discharged alive based on the 7-point ordinal scale on Day 2 through Day 10 as well as last available assessment will be summarized by cohort and overall total.

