Time to recovery based on the 7-point ordinal scale will be modelled using a competing risk analysis. The competing event is death. Participants not achieving recovery at the last assessment will be censored on the day of the last clinical assessment. In addition, the cumulative incidence from the competing risk analysis will also be graphically presented. Furthermore, the number and percentage of participants with recovery based on the 7-point ordinal scale on Day 2 through Day 10 as well as last available assessment will be summarized by cohort and overall total.

Clinical improvement based on scoring using the PEWS Improvement Scale

For each cohort and overall total, clinical status and change from Baseline in clinical status by Study day will be summarized for the number and percentage of participants for each PEWS improvement scale category (behavior, cardiovascular, respiratory) as well as total score. It should be noted that the main timepoint of interest for this endpoint is Day 10. A stacked bar chart will also be provided for each cohort and overall total for each PEWS improvement scale category (behavior, cardiovascular, respiratory) depicting the percentage of participants for each category by Study Day.

Time to ≥ 2 -point improvement or discharged alive will be modelled using a competing risk analysis for each PEWS improvement scale category (behavior, cardiovascular, respiratory). The competing event is death. Participants not achieving ≥ 2 -point improvement at the last assessment will be censored on the day of the last clinical assessment. In addition, the cumulative incidence from the competing risk analysis for each PEWS improvement scale category (behavior, cardiovascular, respiratory) will also be graphically presented. The number and percentage of participants with a ≥ 2 -point improvement or discharged alive on Day 2 through Day 10 or discharged alive for each PEWS improvement scale category (behavior, cardiovascular, respiratory) will also be summarized by cohort and overall total.

Time to \geq 1-point improvement or discharged alive will be modelled using a competing risk analysis for each PEWS improvement scale category (behavior, cardiovascular, respiratory). The competing event is death. Participants not achieving \geq 1-point improvement at the last assessment will be censored on the day of the last clinical assessment. In addition, the

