- b) The month and year (or year) of the onset date is the same as or before the month and year (or year) of the 30th day after the date of the last dose of study drug, and
- c) End date is as follows: The (complete) end date is on or after the first dose date, or The month and year (or year) of end date is the same or after the month and year (or year) of the first dose of study drug, or End date is completely missing

Events with Completely Missing Onset Date

• An AE with a completely missing onset date is defined as TEAE if end date meets any of the 3 criteria specified above.

14) The precision in reporting numerical values should be as follows:

- Raw measurements will be reported the same as the data captured electronically or on the eCRF.
- Standard deviation and standard error will be reported to one more significant decimal place than the raw measurement.
- Mean, median, minimum, Q1, Q3, maximum, 95% CIs will be reported to the same number of decimal places of the raw measurements.
- Exceptions may be considered; for example, if more than 4 significant digits are provided for the measurement.
- 15) Last dose date is not expected to be missing. However, if last dose date is missing due to data issues, it will be imputed using the maximum of non-missing, non-zero dose, study drug start and stop dates.

16) Ordinal scale and oxygen support status

• The Ordinal Scale is an assessment of the clinical status of a given study day. Each day, the worst (ie, lowest ordinal) score from the previous day will be recorded (ie, on Day 3, the lowest ordinal score from Day 2 is obtained and recorded for Day 2). The original Ordinal Scale (A to G) has been converted to a 7-point scale with the associated oxygen support status defined in the following table:

Ordinal Scale		Oxygen Support Status	
1	Death	Death	
2	Hospitalized, on invasive mechanical ventilation or ECMO	Invasive Mechanical Ventilation	
3	Hospitalized, on non-invasive ventilation or high flow oxygen devices	High Flow Oxygen	
4	Hospitalized, requiring low flow supplemental oxygen	Low Flow Oxygen	
5	Hospitalized, not requiring supplemental oxygen - requiring ongoing medical care (COVID-19 related or otherwise)	Room Air	
6	Hospitalized, not requiring supplemental oxygen - no longer requires ongoing medical care (other than per protocol RDV administration)	Room Air	
7	Not hospitalized	Discharge	

17) Censoring rules for competing risk analysis

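### After discharge the ordinal score stays at 7 unless the child dies, so a child readmitted by Day 10 would be shown as not hospitalized and recovered

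*SAP*

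**What the plan says.** Section 6.2.1 of the SAP fixes the 7-point ordinal score once a participant has left hospital alive: "the endpoint on the day of discharge alive and all subsequent days through Day 10 will be set to Not hospitalized (=7"). The one exception is death after discharge: "On the day of death and all subsequent days through Day 10, the endpoint will be set to Death (=1"). Neither Section 6.2.1, Section 6.2.2 nor Appendix 3 (items 16 and 17) says what happens on readmission.

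The same section defines ordinal recovery by score: "Recovery is defined as an improvement from a baseline score of 2 through 5 to a score of 6 or 7", or from 6 to 7. Section 6.2.2 summarizes "the number and percentage of participants with recovery based on the 7-point ordinal scale on Day 2 through Day 10", and says of the ordinal-scale endpoint that "the main timepoint of interest for this endpoint is Day 10".

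Appendix 3 item 16 describes the scale: "The Ordinal Scale is an assessment of the clinical status of a given study day". Score 7 means not hospitalized. Score 2 is "Hospitalized, on invasive mechanical ventilation or ECMO".

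**The concern.** The scale is meant to describe how the child is on each study day. For a readmitted child the rule assigns a category, not hospitalized, that does not describe that day. Because 7 is the top of the scale, the error can only be favourable. The plan already accepts that discharge is not final, since a later death replaces the 7. Non-fatal relapse is the case left out.

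At stake are the descriptive summaries built on the daily score: status by category, change from baseline, the stacked bar chart and the recovery percentage, each by cohort and overall. The study has a single arm, so no comparator carries the same convention.

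**Working it through.** The plan states no figure for this point, so there is none to reproduce. The check applies the rule to a constructed case and then works out the weight of one child.

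**Inputs from the SAP.** Scoring rule, its death exception and the recovery definition: Section 6.2.1. Score meanings: Appendix 3 item 16. Cohort size 12 for Cohorts 1-4 and a total of at least 52: Section 1.3. Cohort 5 size of at least 4: Table 1-1.

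**Constructed case (assumption).** A child is discharged alive on Day 5, then readmitted and invasively ventilated from Day 7 through Day 10.

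- As written: the score is 7 on Days 5-10. Change from baseline at Day 10 = 7 − baseline.
- By actual status: the score is 7 on Days 5-6 and 2 on Days 7-10. Change at Day 10 = 2 − baseline.

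| Baseline | Day 10 change, as written | Recovered? | Day 10 change, actual status | Recovered? |
|---|---|---|---|---|
| 3 | +4 | yes | −1 | no |
| 4 | +3 | yes | −2 | no |
| 5 | +2 | yes | −3 | no |

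Ventilation is only the extreme example. From a baseline of 2 to 5, recovery needs a 6 or 7, so a readmitted child whose true score is anywhere from 2 to 5 is misclassified in the same way.

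**Weight of one child, 1/n.** 1/12 = 8.3 points; 1/52 = 1.9 points; 1/4 = 25 points if Cohort 5 enrols only its minimum. Two children: 2/12 = 16.7 points; 2/52 = 3.8 points.

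**Chance that the case arises.** The SAP gives no readmission rate. With an assumed proportion p readmitted by Day 10, the chance of at least one case is 1 − (1 − p)^n:

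| Assumed p | n = 12 | n = 52 |
|---|---|---|
| 2% | 22% | 65% |
| 5% | 46% | 93% |
| 10% | 72% | 99.6% |

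These rates show a range and are not estimates. At p = 0 the rule does no harm.

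**Which outputs use the post-discharge score.**

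- Affected: status by day and at Day 10, change from baseline, the stacked bar chart and ordinal recovery by day.
- Not affected: time to first improvement, recovery or discharge. The first discharge has already counted as the event.
- Not affected: days of oxygen support. Section 6.2.2 counts them only up to discharge alive, death or Day 10.
- Largely not affected: the percentages with at least 1- or 2-point improvement. Their definitions include discharge alive as an alternative route.

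**The case against.** The strongest defence is that the rule overwrites no scheduled score. Footnote b of Appendix 1 ends the daily evaluations at discharge, so the 7 is a prespecified convention for days on which nothing is scheduled. It is right for every child who stays out of hospital. There is no primary efficacy endpoint (Section 6.1) and no formal testing (Section 3.5). Adverse events are followed to the Day 30 visit and listed, so a serious relapse would probably be visible there. Rebuilding scores after readmission may also mean inventing data. Score 5 covers care for any reason, so a readmission unrelated to COVID-19 would count as loss of recovery.

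Most of this stands, and it keeps the point small. It does not rescue the rule itself: where a readmission is on record, the category not hospitalized is wrong even if the level of support is unknown.

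A reader might also infer that days on oxygen support are understated because of this rule. The SAP does not support that. Those days stop at discharge alive by their own definition, and rescoring would not add any. Nor can one infer that the improvement percentages are clearly inflated, since discharge alive satisfies them whatever score follows.

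**Conclusion.** The concern holds in a limited form. As written, a child readmitted on or before Day 10 would be scored 7 and, from a baseline of 2 to 5 or of 6, counted as recovered while in hospital. This would bias by-day and Day 10 ordinal status, change from baseline, the stacked bar chart and ordinal recovery favourably, by 8.3 points per child in a cohort of 12 and 1.9 points in 52.

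The conclusion rests on two assumptions: that at least one child is readmitted by Day 10, and that recovery on a given day is read from that day's score, which is how Section 6.2.2 is worded. A reader might conclude that the reported results are biased. The document does not show that, because it gives neither a rate nor a count of readmissions. This is a minor gap in a descriptive secondary endpoint.

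**What to change.** In Section 6.2.1, limit the discharge rule to days on which the participant has not been readmitted. From the readmission date, use the recorded in-hospital status where available. Where it is not, do not score 7; treat the child as hospitalized with support level unknown, under a stated convention such as category 5 at best. State this explicitly: Section 6.2.1 also carries the last known status forward over missing days, so simply removing the rule would bring the 7 back. Report the number readmitted by Day 10, by cohort and overall. If it is zero, saying so settles the matter.

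The cost is a sentence or two and one count. Section 1 already provides for changes after SAP finalization to be documented in the CSR. The downside is that support after readmission may be known only approximately. Before adopting the change, confirm that the Hospitalization Information eCRF or the adverse event records capture readmission and its date.
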